8.7. EXACERBATION VISIT/CONTACT

Subjects will be trained by the Investigator to recognise signs and symptoms of NCFB pulmonary exacerbations.

At each post-randomisation visit the patient will be reminded about how to recognise symptoms of a NCFB pulmonary exacerbation and instructed to contact the site as soon as they have experienced these symptoms for 24 hours. If feasible, the subject will be asked to attend the clinic at their earliest convenience. If it is not practical for the subject to make an additional clinic visit then relevant information will be collected via phone and the subject will be asked to send a sputum sample to the clinic.

Any episodes of pneumonia during the trial should be considered as severe pulmonary exacerbations and will also require a clinic visit, if feasible.

The Investigator will decide if symptoms represent a NCFB pulmonary exacerbation meeting the protocol-defined criteria or not and on the appropriate course of action.

It will be clinically determined if the subject requires systemic antibiotic therapy (oral or intravenous) in addition to IMP administration or whether IMP administration should be temporarily interrupted (see below). Treatment of a NCFB pulmonary exacerbation will follow current treatment regimens used in the respective participating trial site.

If subjects need to be admitted to hospital for intravenous antibiotics, they should be visited by the research staff for an assessment within 72 hours of admission (where possible). If the subject is admitted to a hospital that is not the investigational site, the assessments should be carried out (where possible) by the admitting hospital under the direction of the investigational site. These assessments will include those collected during exacerbation visits/contacts and will include details regarding any interruption of IMP administration. In these circumstances, every effort should be made to complete all assessments although it is recognised that this might not be possible.

Telephone calls will be made to patients on a weekly basis during a NCFB pulmonary exacerbation until resolution to assess the progression of symptoms to and to determine whether systemic antibiotic treatment is ongoing. A telephone script will be provided to sites and responses to standardised questions will be collected in relevant eCRFs.

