10.1. RESCUE MEDICATION

Rescue medication for NCFB pulmonary exacerbations allowed in the study include:

- acute and/or short-term administration of oral/intravenous bronchodilators and corticosteroids, if required;
- systemic (oral or intravenous) antibiotics according to current treatment regimens used at the participating sites;
- acute and/or short-term administration of oxygen therapy/ventilator assistance.

At each visit subjects will be asked about any rescue medications they have taken to self-treat at home.

Rescue medication prescribed by the Investigator for a pulmonary exacerbation will be documented.

The following will be recorded:

- Dates of administration including start and end dates;
- Dosage information including dose and frequency;
- Reason for use.

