In the case of a partial onset date of NCFB pulmonary exacerbation due to missing day, the onset of the event will be assumed to be the first day of the month. If the resultant derived date is prior to the date of first IMP dose, then it will be assumed to be equal to the first IMP dose date. Resultant derived dates will be reviewed during the blind review meeting and documented in the Blind Data Review and Analysis Sets Report.

In case of a partial resolution date of NCFB pulmonary exacerbation due to missing day, the resolution of the event will be assumed to be the last day of the month. If the resultant derived date is after the treatment completion/discontinuation date, then it will be assumed to be equal to the treatment completion/discontinuation date.

In case a NCFB pulmonary exacerbation presents a symptom with missing duration, following a conservative approach, the longest duration based on the start and stop dates of that symptom and until the resolution date of the NCFB pulmonary exacerbation will be imputed.

Two NCFB pulmonary exacerbations will be considered as a single episode in the statistical analysis if the second exacerbation started less than 14 days after the end of the systemic antibiotic therapy for the previous exacerbation (start date of the exacerbation - end date of the treatment of the previous exacerbation < 14 days). In case of more than two exacerbations for the same subject, this rule will be applied iteratively (therefore, more than two exacerbations may be considered as a single episode). Such cases will be discussed during the blind review of the data and the decisions taken will be documented in the Blind Data Review and Analysis Sets Report.

The above rule will not apply to the analysis of NCFB pulmonary exacerbations as AEs in the safety analysis.

In case of NCFB pulmonary exacerbations considered as a single episode:

- the start date of the first event will be considered as the start date;
- the stop date of the last event will be considered as the stop date;
- a worst case approach will be considered for duration of symptoms and requirement of hospitalisation. For example, if one of two exacerbations considered as a single episode has/have increased dyspnoea for ≥ 24 hours and < 48 hours and the other one has increased dyspnoea for ≥ 48 hours, the single episode will be considered in the analysis as having dyspnoea for ≥ 48 hours.

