The number and the percentage of subjects with 0, 1, 2 or > 2 pulmonary exacerbations will be presented.

The number and the percentage of subjects with pulmonary exacerbations, the number of pulmonary exacerbations and the pulmonary exacerbation rate per subject per year will also be presented by treatment group for severe (defined as those requiring intravenous antibiotics and/or hospitalisation) and not severe exacerbations.

The rate of pulmonary exacerbations per subject per year will be calculated for each treatment using a weighted approach (which consists of pooling all subjects in a treatment group and dividing the total number of pulmonary exacerbations by the total follow-up time).

The total duration of systemic antibiotic therapy, overall and by route, will be summarised by treatment group using descriptive statistics for continuous variables as well as distribution frequencies for the following categorisations:

- 1-7 days;
- 8-15 days;
- 16-30 days;
- > 30 days;
- Not Evaluable.

CONFIDENTIAL

Sponsor:	Zambon S.p.A.	Protocol Number:	Z7224L01
----------	---------------	------------------	----------

Results will be reported overall and by country.

The duration of the treatment will be evaluated considering the start and end date of the therapy associated with the pulmonary exacerbation. The duration of each course of systemic antibiotic therapy will be calculated using the following formula:

- Duration (days) = stop date – start date +1

For exacerbations treated with more than one systemic treatment, the duration will be calculated by summing the duration of the associated treatments. The overlapping days will be counted only once.

It is expected that all systemic antibiotic therapy will have completed (i.e. will have a stop date) at the end of the study when data are final, as all therapy stop dates are required to be known in order to derive the resolution date of pulmonary exacerbations per the definition described earlier in this section.

In order to calculate the duration of each course of systemic antibiotic therapy, the following rules will be applied for partial dates of start and stop date of systemic antibiotic therapies:

For the start date:

- if only the day is missing, the first day of the month will be assumed. If the resulting derived date is prior to the start date of the exacerbation, then start date of therapy will be assumed to be equal to the start date of the pulmonary exacerbation.

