4.7.6.4 CCI

A single endpoint of the number and the percentage of subjects with severe CCI will be presented. CCI documented on the CCI form of the eCRF are presumed to include episodes of pneumonia which require intravenous antibiotics and/or hospitalisation. CCI form of the eCRF that is linked to an adverse event with a Preferred Term of 'Pneumonia' but does not have any associated intravenous antibiotics or hospitalisation will be assumed to be a CCI. Data will be reviewed during the blind review meeting and documented in the Blind Data Review and Analysis Sets Report.

A CCI will be defined as treated with systemic antibiotic therapy if a treatment is recorded in the Systemic Antibiotic Therapy form of the eCRF.

The corresponding adjusted mean annual CCI rate estimated by a negative binomial model with the same characteristics as the primary efficacy model as detailed in Section 4.7.4 will be analysed. The adjusted mean annual CCI in each treatment group and the adjusted rate ratio with their 95% CIs will

CONFIDENTIAL

Sponsor:	Zambon S.p.A.	Protocol Number:	Z7224L01
----------	---------------	------------------	----------

be estimated by the model. An adjusted rate ratio <1 will indicate that colistimethate sodium decreases the rate of CCI compared to placebo. A two-sided Wald chi-square test p-value of <0.05 will be considered statistically significant. P-values of the effects based on Wald chi-square test will also be presented.

The above summary/analysis will be performed using the mITT Population.

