4.13 Changes in Conduct or Planned Analyses from the Protocol

Sections 2.2, 4.4.11, 4.7.5 and 4.7.6.3: The protocol incorrectly referred to the units for the determination of CCI [REDACTED] which have been reported as CCI [REDACTED] by the central laboratory.

Section 3.9: The rationale and results for a reassessment of the original sample size calculation are provided to explain the reduced target sample size and associated levels of power.

Section 4.7.4: The protocol states that the Negative Binomial Model will consider the log-time on study as offset. However, as specified in Section 4.1.7, NCFB Pulmonary Exacerbations analyses focus on the treatment period so log-time on treatment will be considered.

Section 4.7.6.1: The protocol states that CCI [REDACTED] = CCI [REDACTED]. For time-to-event endpoints, generally the + 1 is not included because this overestimates the time by 1 day for every event, therefore "+ 1" has been deleted.

Section 4.7.6.4: The protocol states that any episodes of pneumonia will be considered as severe pulmonary exacerbations. Any reported episodes of pneumonia which do not require intravenous antibiotics and/or hospitalisation will be data queried to amend the Preferred Term. However, any pulmonary exacerbation on the Pulmonary Exacerbation form of the eCRF that is linked to an adverse event with a Preferred Term of 'Pneumonia' but does not have any CCI [REDACTED] or CCI [REDACTED] will be assumed to be a severe NCFB pulmonary exacerbation.

Section 4.7.6.5: The protocol states that the CCI [REDACTED] total score will be computed and analysed. However, as recommended in the Manual Scoring Instructions CCI [REDACTED] only the CCI [REDACTED] domain scores will be presented and analysed.

There have been no other changes in analyses from those defined in the protocol.

CONFIDENTIAL

Sponsor:	Zambon S.p.A.	Protocol Number:	Z7224L01
----------	---------------	------------------	----------

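### The SAP's severity summary defines severe exacerbations without the pneumonia rule used for the tested severe-exacerbation endpoint, so severe counts could disagree

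*SAP*

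**What the plan says.** SAP 4.7.4 asks for the number and percentage of subjects, the number of events and the rate per subject-year, by arm, for "severe (defined as those requiring intravenous antibiotics and/or hospitalisation) and not severe exacerbations". The bracket is closed: it does not mention pneumonia or refer to another section. The outputs are Tables 14.2.1.2.1 (mITT) and 14.2.1.2.2 (PP).

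SAP 4.7.6.4 sets a wider rule for the severe-exacerbation endpoint. An event on the exacerbation form that is linked to Preferred Term Pneumonia but "does not have any associated intravenous antibiotics or hospitalisation will be assumed to be a" is given a label that is blacked out in that section. SAP 4.13, which describes the same rule for 4.7.6.4, prints the label: the event "will be assumed to be a severe NCFB pulmonary exacerbation". The endpoint is analysed in the mITT population with a negative binomial model and a two-sided test at 0.05. SAP 4.7.5 places the secondary endpoints in a testing hierarchy.

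Protocol 8.7 is broader: "Any episodes of pneumonia during the trial should be considered as severe pulmonary exacerbations".

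SAP 4.13 adds a control: "Any reported episodes of pneumonia which do not require intravenous antibiotics and/or hospitalisation will be data queried to amend the Preferred Term". SAP 4.7.6.4 also sends these data to the blind review meeting.

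For records merged into one episode, SAP 4.7.4 says that "a worst case approach will be considered for duration of symptoms and requirement of hospitalisation".

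**The concern.** One term has two definitions in one plan. The event that 4.7.6.4 adds is, by construction, one that 4.7.4 classes as not severe. SAP 4.13 ties the pneumonia rule to 4.7.6.4 only and then says there are no further changes from the protocol. A programmer who follows 4.7.4 literally would therefore produce a severity table that departs from Protocol 8.7 without disclosure.

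What is at stake is consistency of reporting. Both sections report the number and percentage of mITT subjects with a severe event, and those figures should be identical. If they are not, a reader of the report cannot tell which count supports a statement about severe exacerbations. Time to first severe exacerbation is also tested, and 4.7.6.5 leaves two candidate definitions open.

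**Working it through.** The documents state no severe-event rate, count or power, so there is no figure to reproduce. The check is a comparison of texts, followed by an illustration of scale.

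**Step 1: the definitions side by side**

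| Place | IV antibiotics or hospitalisation | Preferred Term Pneumonia with neither |
|---|---|---|
| SAP 4.7.4 (Tables 14.2.1.2.1, 14.2.1.2.2) | severe | not severe |
| SAP 4.7.6.4 with 4.13 (tested rate) | severe | severe |
| SAP 4.7.6.5 (tested time to first severe) | not defined there | not defined there |
| Protocol 8.7 | not addressed | severe (all pneumonia) |

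**Step 2: can such an event exist in the data?** A protocol-defined exacerbation needs systemic antibiotics, and Protocol 10.1 describes these as "systemic (oral or intravenous) antibiotics according to current treatment regimens used at the participating sites". A counted pneumonia without intravenous treatment or admission would therefore in practice be treated orally. That is an inference; the SAP says only that neither feature is present. The query in 4.13 may remove such events by changing the Preferred Term, but 4.13 keeps a rule for any that remain.

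**Step 3: which figures should agree?** The rate in 4.7.4 is total events divided by total follow-up. The rate in 4.7.6.4 is adjusted by a model. Those two rates would differ even under one definition. Severe event counts and n (%) of mITT subjects should be identical.

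**Step 4: scale, on assumed inputs only.** Recruitment closed at 377 subjects (SAP 3.9), or about 188 per arm, so 188 years is roughly the most follow-up one arm can give over one year. I take 150 to 188 years per arm, and 20 or 40 events per arm with intravenous antibiotics or hospitalisation. Both ranges are assumptions.

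- Shift in the arm's pooled severe rate per discordant event = 1 / follow-up years: 1/150 = 0.0067 to 1/188 = 0.0053 per year.
- Pooled rate at 170 years, before and after adding p discordant events = s/170 and (s + p)/170:

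| s | p = 0 | p = 2 | p = 4 | p = 8 |
|---|---|---|---|---|
| 20 | 20/170 = 0.118 | 22/170 = 0.129 (+10%) | 24/170 = 0.141 (+20%) | 28/170 = 0.165 (+40%) |
| 40 | 40/170 = 0.235 | 42/170 = 0.247 (+5%) | 44/170 = 0.259 (+10%) | 48/170 = 0.282 (+20%) |

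The relative change is p/s, whatever the follow-up. For n (%), a subject whose only qualifying event is discordant moves the percentage by 1/188 = 0.5 points. If the query removes every such event, p = 0 and the outputs agree.

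**The case against.** The best defence is that the plan already limits the problem. Sites are queried, the data go to blind review, the severity table is descriptive, and the tested endpoint has its own stated rule that follows the protocol. SAP 4.13 is worded as a classification of the event, and a listing of derived exacerbation data is planned, so one shared flag may be what the sponsor intends. The secondary endpoint lists and some nouns in 4.7.6.4 are redacted, and a general definition could sit there.

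Much of this stands. It limits the size, possibly to nothing, and it rules out saying that the tables will disagree. It does not remove the conflict: the bracket in 4.7.4 is explicit and unredacted, and it contradicts any wider definition elsewhere. Nothing in 4.7.4 carries the pneumonia rule or the outcome of the review into the severity table.

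A reader might infer three stronger points that the documents do not support:

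- **Time to first severe takes the 4.7.6.4 rule by reference.** It does not. SAP 4.7.6.5 refers to 4.7.6.1, for the method. The gap is that no definition is given.
- **The merging rule is a third definition, and an intravenous course in a later record cannot make an episode severe.** The rule says how attributes combine, not what severe means. A merged episode that includes an intravenous course is still one that required it, 4.7.4 already assigns several therapies to one exacerbation, and merged cases go to blind review. The escalation described in Protocol 9.1.5 is continued treatment of the same exacerbation. The list is merely incomplete.
- **Any gap between the two severe rates shows the conflict.** The estimators differ, so only counts and n (%) are evidence. Table 14.2.1.2.2 is PP, while 4.7.6.4 is mITT only, so that table has no direct counterpart.

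**Conclusion.** The point holds in a narrow form. As written, 4.7.4 contradicts 4.7.6.4, 4.13 and Protocol 8.7 on exacerbations that retain Preferred Term Pneumonia and have neither intravenous antibiotics nor hospitalisation. Severe event counts and n (%) of mITT subjects could therefore differ between Table 14.2.1.2.1 and the 4.7.6.4 output, and 4.7.6.5 is undefined on the same point.

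The size is unknown and may be zero. The percentages above rest wholly on assumed follow-up and event numbers and show only that a few events would be visible against a small severe count. The primary endpoint, its test and its power do not depend on severity and are unaffected. The correction is worth making because the rule is stated wrongly, not because a distortion has been shown.

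**What to change.** Derive one severity flag per episode, after merging, from the rule the SAP already has: intravenous antibiotics, hospitalisation, or a linked adverse event with Preferred Term Pneumonia. Replace the bracket in 4.7.4 with a reference to that flag, and cite the same flag in 4.7.6.4 and 4.7.6.5. For clarity, add to the worst-case list for merged records that an intravenous route or a linked pneumonia in any component record carries to the episode. Do not widen the rule to other Preferred Terms: that would change the tested endpoint instead of reconciling a descriptive table with it.

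The SAP addendum states that the database is locked and the study unblinded. The report should therefore say which definition each severity output used and give the number of discordant events by arm. If Tables 14.2.1.2.1 and 14.2.1.2.2 used the narrower bracket, rerun them. The rule stood in the protocol and SAP before unblinding, so applying it throughout is not data-driven.

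The cost is a few lines of text, one derived variable and possibly two reruns. No new data are needed. The not-severe count may fall slightly.

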4.7.4.1 CCI Analysis Using Alternative Definition of NCFB Pulmonary Exacerbation

A CCI analysis will be conducted using an alternative definition of NCFB pulmonary exacerbation for the mITT Population. The re-classification of pulmonary exacerbations will be done during the blind review meeting and documented in the Blind Data Review and Analysis Set Report.

In this CCI analysis, a NCFB pulmonary exacerbation is defined as deterioration in three or more of the following key symptoms for at least 48 hours:

- Cough;
- Sputum volume and/or consistency;

CONFIDENTIAL

Sponsor:	Zambon S.p.A.	Protocol Number:	Z7224L01
----------	---------------	------------------	----------

- Sputum purulence;
- Breathlessness and/or exercise tolerance (dyspnoea);
- Fatigue and/or malaise;
- Haemoptysis;

And:

a physician determines a change in bronchiectasis treatment is required when other potential causes of clinical deterioration have been discounted, i.e. the subject requires a systemic antibiotic therapy due to the NCFB pulmonary exacerbation.

Subjects experiencing NCFB pulmonary exacerbations according to this alternative definition will be identified as those subjects having:

- An AE on the eCRF Adverse Events form with a MedDRA coded Preferred Term of “infective exacerbation of bronchiectasis” that is at least 48 hours in duration (i.e. stop date of AE – start date of AE + 1 \geq 2);
- At least 3 of the above symptoms on the eCRF Pulmonary Exacerbation Symptoms form for the Pulmonary Exacerbation Number corresponding to that AE, where those symptoms all occur between the start and stop dates of the AE;
- At least 1 therapy on the eCRF Systemic Antibiotic Therapy form for the Pulmonary Exacerbation Number corresponding to that AE.

Analysis will be conducted following the same rules and methods as detailed above for the main definition of NCFB pulmonary exacerbations.

4.7.4.2 **CCI** Analysis for Discontinuers

In order to assess the potential impact of missing data on the results of the primary efficacy analysis, **CCI** analyses based on multiple imputation (MI) will be performed on all mITT subjects based on the approach proposed by Keene et al. ^[1].

For all subjects with a follow-up duration shorter than 365 days (i.e., 52 weeks + 1 day), the number of pulmonary exacerbations from the end of the follow-up period up to day 365 will be imputed.

The imputation model will include the following variables: treatment, pooled site, i.e. country, as detailed in Section 4.9.1, and use of stable concomitant therapy with oral macrolides.

The imputation will be performed according to the following strategies:

- missing at random: imputation based on the Missing At Random (MAR) assumption in all treatment groups. This analysis is based on the same assumption behind the model used for the primary efficacy analysis, however, it will allow for the inclusion in the analysis of all mITT patients;
- copy reference: imputation based on the data distribution of the placebo group in both treatment groups. This analysis mimics the case where discontinued subjects are in effect non-responders.

One thousand imputations will be performed and the analysis of the total number of pulmonary exacerbations (observed + imputed events) will be based on the same negative binomial model

CONFIDENTIAL

Sponsor:	Zambon S.p.A.	Protocol Number:	Z7224L01
----------	---------------	------------------	----------

used for the primary efficacy analysis. Estimates from the models will then be combined using Rubin's rule ^[2].

